**Statistical analysis plan (SAP) for the (cost-)effectiveness of:
an innovative, personalised intervention of therapeutic Virtual
Reality (VR) IntEgrated within physioTherapY for a subgroup of
complex chronic low back pain (CLBP) patients (VARIETY-study)**

Publication date: 27-01-2023

Sponsor: ZonMw (10270032021502)

Document version: 1.0

Trial registration: ClinicalTrials.gov (ID: NCT05701891)

Main applicant:

[name], HAN

Principal investigator:

[name], HAN

Co-applicants:

[name], VU

[name] [name], Maastricht University

[name] [name], HAN

[name] [name], Radboudumc

[name] [name], Radboudumc

Study objectives and outcomes

Main objective

- To evaluate the effectiveness of physiotherapy with integrated multimodal VR for patients with complex CLBP, compared to usual primary physiotherapy care on physical functioning evaluated by the Oswestry Disability Index (ODI) at 3 months (primary end-point) and 12 months follow-up.

Secondary objective

- To evaluate the effectiveness of physiotherapy with integrated multimodal VR for patients with complex CLBP, compared to usual primary physiotherapy care on secondary outcome measures pain intensity, pain related fears, pain self-efficacy, physical activity level, global perceived effect and problems with activities at 3 months (primary end-point) and 12 months follow-up.
- To evaluate the cost-effectiveness of physiotherapy with integrated multimodal VR for patients with complex CLBP, compared to usual primary physiotherapy care for the 12-month period.

Trial methods

Design

- This study is a pragmatic, multicenter, two-arm, parallel, superiority, cluster-randomized controlled trial. Outcome variables will be measured at baseline, after 1 month (T1; during treatment), 3 months (T3; directly post-treatment), 6 months (T6; 3 months post-treatment) and 12 months (T12; 9 months post-treatment) follow-up, as described in table 1.

Randomization

- Eligible physiotherapists will be randomized on practice level using an online software program and stratified for completion of the three-year master to specialize as a psychosomatic physiotherapist.

Allocation

- Patients will be treated by their physiotherapist and follow the intervention their physiotherapist was randomized to.

Blinding

- Patients cannot be blinded, but will only be informed about their own intervention and will neither be informed about the presence of two arms in the trial nor the intervention received in the other arm.

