- Blinding of participating physiotherapists is not possible, due to the nature of the intervention.
- Blinding of coordinating researchers is not possible, as they need information about treatment allocation for adequate study coordination.
- Blinding of the analyses will be achieved by an independent statistician blinded for treatment allocation, who will perform the primary study analyses.

Sample size

- A clinically relevant between-group difference of at least 10 points on the ODI after 3-months follow-up is expected, which seems plausible based on recent pilot studies with VR from our research group and others. For this expected and clinically relevant difference of 10 and a standard deviation of 15, 60 patients are needed per group ($\alpha=0.05$; power=90%; ICC for clusters 0.05; 15% drop-out). We expect to include 1 patient every 2 months per physiotherapist. A total of 20 participating physiotherapists will result in a total of 120 patients after 12 months.

Time schedule

- This study will start in the first quarter of 2023. Data collection will last until the first quarter of 2025.
- Approval from the medical-ethical committee (METC Oost-Nederland) was granted (case number: 2022-15794).
- The trial was registered with ClinicalTrials.gov (ID: NCT05701891).

Statistical principles

- All analyses in this plan are a priori analyses in that they have been defined in the protocol.
- All outcomes are analyzed for superiority of the experimental group in favor of the control group.
- All analyses described in the plan will take place after database locking, which will occur once all participants have finished their final measurement. An independent statistician that will be blinded for allocation will perform the main analyses.
- All statistical tests will be two-sided and the nominal p-value will be reported. All confidence intervals presented will be 95% and two-sided. The assumption of normal distribution will be checked by visual inspection of Q-Q plots. For skewed data, the interquartile range will be reported.
- Statistical significance is claimed if the null hypothesis is rejected at the significance level (alpha) of $p \leq 0.05$ (one-sided).
- Continuous variables will be summarized by means and SDs in case of a normal distribution and by median and interquartile range in case of a skewed distribution.
- Categorical variables will be summarized by frequencies and percentages.

Hypotheses

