- Participating patients will be described using the following baseline characteristics: age, sex, BMI, tobacco use, duration of complaints, comorbidities, occupation, education level, diagnostic and therapeutic procedures in past 6 months, medication use and experience with VR for treatment and entertainment, as shown in table 2. Moreover, participants will be described using the following clinical outcome measures: physical functioning, pain intensity, pain related fears, pain self-efficacy, physical activity level, problems with activities and intervention expectations.
- Participating physiotherapists will be described using the following baseline characteristics: age, gender, number of years' experience as a physiotherapist and specialization (i.e. finished with a master's degree), as shown in table 3.

Process evaluation

- The following process parameters regarding the physiotherapy treatment will be monitored by the physiotherapists for both arms: number of sessions, duration of sessions, applied treatment modality per session and adverse events (if applicable).
- In the experimental arm, the following VR related parameters will be additionally monitored using an online dashboard: treatment modality, daily treatment duration and VAS pain score (before and after VR use).

Analysis

Primary analysis

- The primary analysis will be an intention-to-treat, longitudinal mixed-model analysis comparing the effectiveness of physiotherapy with integrated multimodal VR for patients with complex CLBP, compared to usual primary physiotherapy care on physical functioning at 3 months (primary end-point) and 12 months follow-up.
- All participants in this study will be analyzed using mixed-models with maximum likelihood estimation.
- The analysis will be adjusted for important prognostic characteristics that potentially confound the treatment effects (e.g. physical functioning, pain severity, pain-related fears, BMI, tobacco use) and the baseline value of the outcome measure, with addition of other patient and/or physiotherapist characteristics that substantially differ between the two arms at baseline.

Secondary analysis

- Clinical effectiveness on secondary outcome measures:

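### The primary mixed model is set to maximum likelihood, with at most 20 randomised practices and no small-sample correction; if z-based inference is used, the two-sided 5% error rate becomes about 6–8%

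*SAP*

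**What the plan says.** The SAP section Primary analysis describes the model in these words: "The primary analysis will be an intention-to-treat, longitudinal mixed-model analysis". It then fixes the estimator: "All participants in this study will be analyzed using mixed-models with maximum likelihood estimation". The adjustment set is the baseline value of the outcome, several named prognostic variables, and any patient or physiotherapist characteristics found to differ between arms. The section Secondary analysis applies the same method to the other clinical outcomes.

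On the number of clusters, the section Randomization says: "Eligible physiotherapists will be randomized on practice level using an online software program". The section Sample size adds: "A total of 20 participating physiotherapists will result in a total of 120 patients after 12 months".

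The SAP names no restricted maximum likelihood (REML), no degrees-of-freedom method and no reference distribution for the mixed model. It also does not say whether practice enters the model as a random effect; the ICC appears only in the sample-size assumptions ("power=90%; ICC for clusters 0.05; 15% drop-out").

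**The concern.** ML estimates variance components as if the fixed effects were known. With few clusters this makes the between-practice variance too small. With many covariates it does the same to the residual variance. The standard error of the arm effect then comes out too small. If that standard error is also referred to the normal distribution, about 18 cluster-level degrees of freedom (20 practices less two arm means) are treated as infinite.

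The result affected is the superiority claim on the ODI at 3 months. The p-values would be too small and the 95% confidence intervals would cover less often than stated, and the secondary outcomes analysed in the same way would share the problem. Adding a practice random intercept does not remove it, because the error arises in how that intercept's variance is estimated and tested.

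**Working it through.** **Inputs from the SAP.** Recruitment: "We expect to include 1 patient every 2 months per physiotherapist". Sample size: "For this expected and clinically relevant difference of 10 and a standard deviation of 15, 60 patients are needed per group", with "power=90%; ICC for clusters 0.05; 15% drop-out".

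**The plan's own figures.**
- Patients: 12 months / 2 = 6 per physiotherapist, and 20 × 6 = 120, as stated. After 15% drop-out, 120 × 0.85 = 102, or 102 / 20 = 5.1 per physiotherapist.
- Sample size: n = 2(z₁ + z₂)² × (15/10)² per group, with design effect 1 + (6 − 1) × 0.05 = 1.25. Two-sided 5%: 47.3 × 1.25 = 59.1 before drop-out and 59.1 / 0.85 = 69.5 after it. One-sided 5%: 38.5 × 1.25 = 48.2, and 48.2 / 0.85 = 56.7. The stated 60 thus matches the two-sided figure before drop-out or, roughly, the one-sided figure after it. That is a separate matter; only the inputs are used here.
- Clusters: 20 physiotherapists randomised by practice give at most 20 practices, and fewer if any practice supplies two.

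**Approximation on cluster means, 20 practices, arm only.** The correct reference is t with 18 df. Using z with an unbiased variance, P(|t₁₈| > 1.96) = 6.6%. ML also shrinks the variance by 18/20, so the test rejects when |t₁₈| > 1.96 × √0.9 = 1.86, which has probability 7.9%.

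**Simulation under no effect.** 102 patients, ICC 0.05, practice random intercept, nominal two-sided 5%. The one-time-point model used 10,000 runs per cell, with 1 or 6 patient covariates and, in some cells, 2 practice-level covariates. The longitudinal model used 6,000 runs, measurements at 1, 3 and 12 months, practice and patient intercepts, arm by time and 6 covariates, and tested the arm effect at 3 months. The Monte Carlo standard error is about 0.3 points. Practice counts below 20 are assumptions.

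| Practices (k) | ML, z: one time point | ML, z: longitudinal | ML, t(k−2): longitudinal | REML, z: longitudinal | REML, t(k−2): longitudinal |
|---|---|---|---|---|---|
| 20 | 6.8–8.2% | 7.3% | 5.1% | 5.7% | 4.1% |
| 16 | 7.3–8.9% | 6.9% | 4.9% | 5.5% | 3.8% |
| 12 | 7.7–10.3% | 7.8% | 4.6% | 5.9% | 3.3% |
| 10 | 9.0–10.6% | 8.3% | 4.4% | 6.2% | 3.1% |
| 8 | 9.8–12.5% | 10.2% | 3.8% | 7.2% | 2.6% |

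Separate simulations agree. ML with z at 20 practices gave 6.2% with arm only, 6.9–7.9% with stratum and 6 or 9 covariates, and 7.6% in a further run with stratum and 6 covariates (9.4% at 10 practices).

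**Standard errors.** In the one-time-point model, the mean ML standard error divided by the true SD was 0.91–0.95 at 20 practices and 0.84–0.91 at 10. For REML it was about 0.99–1.01.

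**Estimator against reference (longitudinal, 20 practices).** Changing only the reference takes 7.3% to 5.1%. Changing only the estimator takes it to 5.7%. Changing both takes it to 4.1%. Both contribute. In the one-time-point model at 20 practices, ML with t(k−2) gave 5.1–6.5% and the ML likelihood-ratio test 5.7–7.2%.

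**Sensitivity to the ICC.** At ICC 0, ML with z gave 4.9–6.4% (one time point, 8–20 practices). At ICC 0.10 the longitudinal figures were 7.3% at 20 practices and 9.5% at 10.

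**Interval width at 20 practices.** t₁₈/z = 2.10/1.96 = 1.07. Adding the correction of the standard error gives 1.07/0.95 = 1.13 to 1.07/0.91 = 1.18.

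**The case against.** The strongest reply is that the SAP names no reference distribution. The 6–8% needs z-based inference; with ML and a cluster-level t the rate at 20 practices is close to nominal, and slightly below it (4.6%) in the arm-only simulation. This stands as a limit on the size of the point. It does not remove the bias in the standard error, which belongs to the estimator.

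Second, the figures describe a model with a practice intercept, which the SAP does not name. That is correct. Whether practice is fitted is a separate and prior question, and the figures here show what remains once it is fitted.

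Third, the sentence may be meant only to say that likelihood-based estimation keeps participants with incomplete follow-up. That is possible, but REML keeps them as well, and as written the text directs the statistician to ML.

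Fourth, the two-sided 5% used here is a choice. The SAP calls its tests two-sided, yet labels as one-sided the threshold introduced by "Statistical significance is claimed if the null hypothesis is rejected at the significance level (alpha) of". At one-sided 5% the longitudinal ML rate at ICC 0.05 is 6.2% with 20 practices and 8.4% with 8, a smaller excess.

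A reader might infer that naming ML by itself raises the error rate to 6–10%. The SAP does not support this: it does not state z-based inference, and the top of the range needs about 10 practices, a number it never gives. A reader might also infer that replacing ML by REML settles the matter. It does not, because small-sample degrees of freedom correct only for random effects that are in the model.

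**Conclusion.** The point holds in a conditional and modest form. The SAP fixes an estimator that is poorly suited to at most 20 clusters and adds no correction. With practice fitted and an ICC of 0.05, ML standard errors are about 5–9% too small at 20 practices. If z-based inference follows, the two-sided 5% error rate is about 6–8%, an excess of roughly 1 to 3 points, and it rises to about 10% if there are only some 10 practices. The cause is shared between the estimator and the reference distribution, so the two should be specified together. If the true ICC is near 0 there is little to correct, but the SAP itself plans for 0.05. It should be put right before database lock, as part of stating the cluster term; on its own it does not overturn the design.

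**What to change.** Replace the sentence on maximum likelihood with: *Mixed models will be fitted by restricted maximum likelihood (REML) with random intercepts for practice and for patient (repeated measures), and with Kenward-Roger (or Satterthwaite) degrees of freedom for tests and confidence intervals.* Apply it to the primary and the secondary mixed models. Naming practice is essential, since without it the degrees-of-freedom method has no cluster level to act on.

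The cost is one sentence and one software setting. At 20 practices, intervals become about 13–18% wider than under ML with z if cluster-level degrees of freedom apply, with a correspondingly small loss of nominal power. Kenward-Roger and Satterthwaite were not simulated. They are expected to fall between REML with z (5.6–6.5% at 20 practices) and REML with t on k − 2 degrees of freedom (4.1–4.8%). The latter is conservative with fewer practices: 1.3–4.2% at 8–16.

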- This study is designed to assess the superiority of physiotherapy with integrated multimodal VR for patients with complex CLBP, compared to usual primary physiotherapy care on physical functioning at 3 months (primary end-point) and 12 months follow-up.
- The null hypothesis is that participants in the experimental group report a similar physical functioning score at 3 months and 12 months follow-up, as participants in the control group.
- The alternative hypothesis is that participants in the experimental group report a significantly higher score on physical functioning at 3 months and 12 months follow-up, as participants in the control group.

Analysis population

We will use the following definitions of analysis populations:

- The intention-to-treat population is defined as all participants provided informed consent and randomized to treatment.
- The per-protocol population is defined as all participants without minor and major protocol deviations.

We will decide which analysis populations each patient belong to in advance of database locking.

Protocol deviations

Major deviations

- For both treatment arms:
 - A total of <4 physiotherapy sessions or >30 physiotherapy sessions during intervention period (recommended: 8 – 25 sessions).
 - None of treatment modalities during the intervention period were exercise therapy or pain education.
 - Patient received invasive treatment (e.g. operation, injection or nerve block) for CLBP during intervention period.
- Specifically for experimental arm:
 - <300 minutes of VR use (50% of minimal dosage) during intervention period.

Minor deviations

- Specifically for experimental arm:
 - <480 minutes of VR use (80% of minimal dosage) during intervention period.

Trial population

- The following figures will be presented in a flow diagram, based on the CONSORT recommendations (figure 1):
 - Number of potentially eligible participants screened by the physiotherapist

- Number of included participants
- Reasons for non-inclusion
- Reasons for loss to follow-up and withdrawal
- Final inclusions in intention-to-treat analysis

Baseline patient and physiotherapist characteristics

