 - The secondary effectiveness analysis will be performed similarly as the primary effectiveness analysis: an intention-to-treat, mixed-model analysis, to evaluate the effectiveness of physiotherapy with integrated multimodal VR for patients with complex CLBP, compared to usual primary physiotherapy care on pain intensity, pain related fears, pain self-efficacy and problems with activities at 3 months (primary end-point) and 12 months follow-up.

Cost-effectiveness

- Health-related Quality of Life: At baseline, 3, 6, and 12 months after start of the intervention, the participants' health states were assessed using the EuroQol 5D Health Questionnaire 3-level version (EQ-5D-5L). Using the Dutch EQ-5D-5L tariff, these health states were converted into utility values (0=dead; 1=full health). Quality-adjusted life-years (QALYs) were calculated using the area under the curve approach.
- Costs: In line with Dutch guidelines, costs were assessed from a societal perspective, meaning that all costs were included irrespective of who paid or benefited.

- Data on other healthcare utilization, informal care, unpaid productivity, and absenteeism. For the cost-utility and -effectiveness analyses, all participants included in the study will be analyzed, with missing data handled by using Multivariate Imputation by Chained Equations (MICE) and the number of imputed datasets will be determined using the loss of efficiency approach. Imputation models will include all available cost and effect measure values as well as variables differing between groups at baseline, variables related to the “missingness” of data and variables related to the outcomes. Pooled estimates will be calculated using Rubin’s rules.

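### Maximum likelihood does not by itself keep patients with a missing baseline covariate, so the promise to analyse all participants is not secured; ML also understates variance when practices are few

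*SAP*

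**What the plan says.** In the SAP's Primary analysis section the main comparison is described as follows: "The primary analysis will be an intention-to-treat, longitudinal mixed-model analysis". The next bullet adds: "All participants in this study will be analyzed using mixed-models with maximum likelihood estimation". The Analysis population section sets the reference group: "The intention-to-treat population is defined as all participants provided informed consent and randomized to treatment".

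The model is adjusted for prognostic variables, given as examples: "e.g. physical functioning, pain severity, pain-related fears, BMI, tobacco use) and the baseline value of the outcome measure". The list is then left open, "with addition of other patient and/or physiotherapist characteristics that substantially differ between the two arms at baseline". The secondary outcomes are to be analysed in the same way.

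The only rule for missing data stands under Cost-effectiveness and is limited to that purpose: "For the cost-utility and -effectiveness analyses, all participants included in the study will be analyzed, with missing data handled by using Multivariate Imputation by Chained". That method is MICE, with results pooled by Rubin's rules. The SAP has no rule for a missing baseline covariate in the primary or secondary mixed models. Nor does it name the random effects, the reference distribution for the test or the number of practices.

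**The concern.** A mixed model fitted by maximum likelihood uses every follow-up ODI that was observed, and under missing at random this is valid for patients whose series is incomplete. The protection concerns the outcome. The model is conditional on the covariates, so standard software removes a patient who lacks any one of them from every visit, even when ODI follow-up is complete. With several questionnaires among the covariates and an open list, the number removed cannot be known in advance. A physiotherapist characteristic could also enter; at 120 patients for 20 physiotherapists, one missing value there would remove about 6 patients.

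These patients do carry outcome information, so losing them costs precision that could be kept. It would also mean that the crude and adjusted columns of Table 4 rest on different patients.

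The same bullet fixes maximum likelihood as the estimator. ML variance components make no allowance for the fixed effects that were estimated. In a cluster-randomised trial with few practices, the standard error of the treatment effect is then too small.

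**Working it through.** **Inputs from the SAP (Sample size section).** Difference 10, SD 15, ICC 0.05, drop-out 15%, 60 patients per group, 20 physiotherapists, 120 patients. Derived: 120/20 = 6 per physiotherapist; after drop-out 60 × 0.85 = 51 per arm and 6 × 0.85 = 5.1 per cluster.

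**The plan's own figure.** With 6 per cluster the design effect is 1 + 5 × 0.05 = 1.25. One-sided at 5%: 39 × 1.25 = 48.75, rounded up to 49; 49/0.85 = 57.6, rounded up to 58, close to the stated 60. Two-sided: 47.28 × 1.25 = 59.1; 59.1/0.85 = 69.5, so 70. The SAP states both one-sided and two-sided testing. That is a separate matter; the power figures below are two-sided unless noted.

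**1. Missing covariates.** The SAP gives no rate, so a range is assumed. The examples amount to six covariates: ODI, NRS, FABQ and PCS (Table 4 lists both under pain-related fears), BMI and tobacco use. Let each be missing in a share p of patients.

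- Share lost if all gaps fall in the same patients: p.
- Share lost if gaps are independent: 1 − (1 − p)^6.
- SE = 15 × √(2 × (1 + (m − 1) × 0.05)/n), with n = 51 × (1 − loss) and m = 5.1 × (1 − loss).
- Power = Φ(10/SE − 1.96).

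With no loss: 1 + 4.1 × 0.05 = 1.205; SE = 15 × √(2.41/51) = 3.26; power = Φ(3.067 − 1.96) = 86.6%.

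| p | Pattern | Lost | n per arm | SE | SE ratio | Power |
|---|---|---|---|---|---|---|
| none | – | 0% | 51.0 | 3.26 | 1.00 | 86.6% |
| 1% | overlapping | 1% | 50.5 | 3.27 | 1.00 | 86.3% |
| 2% | overlapping | 2% | 50.0 | 3.29 | 1.01 | 86.0% |
| 3% | overlapping | 3% | 49.5 | 3.30 | 1.01 | 85.8% |
| 1% | independent | 5.9% | 48.0 | 3.34 | 1.02 | 84.9% |
| 2% | independent | 11.4% | 45.2 | 3.42 | 1.05 | 83.2% |
| 3% | independent | 16.7% | 42.5 | 3.51 | 1.08 | 81.3% |

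One-sided (1.645 in place of 1.96), power is 92.3% with no loss and 88.6% in the last row.

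A simulation (20 clusters of 6, three follow-up visits, covariate values missing completely at random) compared deletion with filling in the covariate mean. At 5, 10 and 20% missing, the SE ratio was 1.03, 1.05 and 1.10. Both estimates stayed at about −10, the simulated effect. The cost in that setting is precision, and imputation recovers it.

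**2. ML with few practices.** Assumptions: a practice effect is in the model, the ICC is 0.05, and the test is a Wald z. The number of practices is not stated. With 20 physiotherapists randomised by practice, 20 is taken as the upper end and 10 as a scenario. In a balanced design with k practices, ML divides the between-practice sum of squares by k instead of k − 2. Without the constraint that the practice variance cannot be negative, the SE would be √(18/20) = 0.95 or √(8/10) = 0.89 of its true value. That constraint lessens the shortfall, as the simulations show:

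| Practices × patients | ML: SE too small by | ML, z | ML, t on k − 2 | REML, z |
|---|---|---|---|---|
| 20 × 6 | about 3% | 6.2 to 6.5% | about 4.8% | about 5.5% |
| 10 × 12 | about 8% | 8.2 to 8.7% | about 4.6% | about 6.6% |

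The last three columns are type I error at a nominal two-sided 5%. The ranges cover a two-level model and a three-level model (practice, patient, three visits; patient variance share 0.5, assumed). REML with Satterthwaite degrees of freedom gave about 4.5 to 4.6% in the three-level model.

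**The case against.** **Deletion is not stated.** A reader might infer that the model drops anyone with an incomplete record and that intention-to-treat is therefore not delivered. The SAP does not support that. It states the intention to include everybody and nowhere says that incomplete cases are removed. Deletion is a software default, a joint likelihood for outcome and covariates could keep such patients, and the protocol, not shown, may hold a rule. What stands is that the SAP names a method that does not do this by itself.

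**Patients without any follow-up ODI.** It is tempting to count them as a loss too. In a baseline-adjusted likelihood they carry no information on the treatment effect, and the fit without them is the same and valid under missing at random. The flow diagram is already to show losses and the final intention-to-treat numbers. Only the wording is at issue for them.

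**The power figures are near the unfavourable end.** The named covariates are all collected at baseline, so gaps may well coincide, and the upper rows of the first table then apply. The calculation also gives the covariates no credit for explaining variance. If they correlate 0.4 with follow-up ODI (assumption), power is 91.7% with no loss and 90.4, 89.0 and 87.5% under independent gaps, all above 86.6%. This is right about the absolute level. The relative rise in SE from losing patients stays.

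**Bias.** Differential completeness between unblinded arms is conceivable, but these are baseline measures, patients are not told of a second arm, and nothing in the SAP suggests it.

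**Two ODI effects.** Table 6 reports an ODI effect from imputed data. That is not a contradiction: it comes from a different model, is labelled as imputed and serves the cost-effectiveness ratio.

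**ML against REML.** The inflation depends on a z test that the SAP does not specify, and a t reference on practices minus 2 removes it even under ML. This stands: the degrees of freedom do most of the work for the test. REML corrects the standard error itself, but with a z test it still exceeds 5%, which is why the two belong together.

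**Conclusion.** The point holds as a gap between a stated property and the stated method. The bullet promises that everyone is analysed; maximum likelihood with an open covariate list does not secure this, and the imputation that would is reserved for the economic analyses. On the assumption of six covariates each missing in 1 to 3% of patients, the loss runs from 1 to 3% (gaps coincide) to 6 to 17% (gaps independent), and the SE rises by between less than 1% and about 8%. If baseline data are nearly complete, the effect is negligible.

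The choice of ML is a second, smaller defect in the same sentence. Its size, an SE 3 to 8% too small and type I error of about 6 to 9%, rests on a practice effect in the model, ICC 0.05, a z test and 20 to 10 practices.

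Neither part shows that the trial's conclusion would be biased or that the intention-to-treat analysis fails. Both can be corrected almost without cost before database lock.

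**What to change.** 1. State that missing baseline covariates will be imputed for the primary and secondary mixed models, either by single imputation from baseline data or from the MICE data sets already planned, so that nobody with a follow-up ODI is lost.
2. Replace maximum likelihood by REML with Satterthwaite or Kenward-Roger degrees of freedom.
3. Reword the bullet so that the model is said to include all participants with at least one follow-up ODI (for a secondary outcome, at least one follow-up value of that outcome).

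The cost is SAP wording and one extra imputation step. Intervals become slightly wider under REML with small-sample degrees of freedom. No new data or patients are needed.

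### The stratification factor (psychosomatic master) is not named in the primary or secondary mixed models; if it is prognostic and clusters are modelled, the reported standard error is somewhat too large

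*SAP*

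**What the plan says.** SAP, Randomization: allocation is at practice level and "stratified for completion of the three-year master to specialize as a psychosomatic physiotherapist".

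SAP, Primary analysis: the model adjusts for "important prognostic characteristics that potentially confound the treatment effects (e.g. physical functioning, pain severity, pain-related fears, BMI, tobacco use"), for the baseline value of the outcome, and "with addition of other patient and/or physiotherapist characteristics that substantially differ between the two arms at baseline". Estimation is fixed by "All participants in this study will be analyzed using mixed-models with maximum likelihood estimation". No cluster random effect and no degrees-of-freedom method is stated.

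SAP, Secondary analysis: "The secondary effectiveness analysis will be performed similarly as the primary effectiveness analysis".

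SAP, Baseline patient and physiotherapist characteristics: the described features include "experience as a physiotherapist and specialization", and Table 3 has a row for the psychosomatic specialisation. Neither place makes it a model term.

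**The concern.** A factor used to constrain randomisation is normally carried into the analysis. Here every named covariate belongs to the patient. A physiotherapist characteristic has one stated way in, through an observed difference between arms, and stratification exists to prevent that difference for this factor. The rule is therefore least likely to pick up the one physiotherapist characteristic the design treats as important. If it does enter, through the open list or a chance imbalance, that is a choice made after seeing data, although the SAP says under Statistical principles that its analyses are a priori.

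What is at stake is efficiency. Stratification removes the factor's contribution to the difference between arms. A model that fits a cluster effect but omits the factor still counts its variance as between-cluster error. The standard error then overstates the real uncertainty, and the benefit of stratifying is not credited in the confidence interval.

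**Working it through.** **Inputs from the SAP (Sample size).** Difference 10 ODI points, SD 15, "ICC for clusters 0.05; 15% drop-out", and 20 physiotherapists with 120 patients, so 120/20 = 6 patients each.

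**The plan's own figure.** Two-sided 0.05 and 90% power: 2 × (1.960 + 1.282)² × 15²/10² = 47.3 per group. Design effect 1 + (6 − 1) × 0.05 = 1.25, and 47.3 × 1.25 = 59.1, which gives the stated 60 before drop-out. With drop-out it would be 59.1/0.85 = 69.5. That mismatch is a separate matter; nothing below depends on it.

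**Assumptions (not in the SAP).** Stratum effect of 0, 3 or 5 ODI points; 40% of clusters specialised (30 to 50% as a range), equally in both arms; each physiotherapist is one cluster; a cluster effect is modelled; single time point; two-sided 0.05.

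**Variance components.** Between clusters: 0.05 × 225 = 11.25. Within: 213.75. A stratum effect b with proportion p specialised has variance b²p(1 − p).

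**5 points, p = 0.4, total ICC held at 0.05.**
- Stratum variance: 25 × 0.24 = 6.00. Remaining between-cluster variance: 11.25 − 6.00 = 5.25.
- Variance of a cluster mean given the stratum: 5.25 + 213.75/6 = 40.875.
- Standard error with the term: √(2 × 40.875/10) = 2.86.
- Standard error reported without it: √(2 × (40.875 + 6.00 × 10/9)/10) = 3.08.
- 95% CI width ratio with t on 18 v 17 df: (2.101 × 3.084)/(2.110 × 2.859) = 1.07.

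**Simulation (cluster-mean t-test, 200,000 runs per cell, p = 0.4).** Power for a 10-point treatment effect:

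| Stratum effect | Omitted | Included |
|---|---|---|
| 0 | 0.870 | 0.868 |
| 3 | 0.874 | 0.883 |
| 5 | 0.881 | 0.909 |

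At 5 points the empirical SD of the estimate is 2.86 with or without the term; the mean reported standard error is 3.04 without it and 2.82 with it. Type I error is 0.036 v 0.050. Only the reported precision differs, and the test without the term is conservative.

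**Sensitivity at 5 points.**
- ICC of 0.05 taken as excluding the stratum: 0.838 v 0.868.
- Five analysed patients per cluster (about 15% drop-out): 0.827–0.830 v 0.854–0.861.
- One-sided 0.05, which Statistical principles also states: 0.941–0.943 v 0.954–0.957.
- Ten practices of 12 patients: 0.727 v 0.805 (at 0 points, 0.729 v 0.712).
- No cluster effect fitted, patients treated as independent: the CI ratio is about √(225/219) = 1.014, and the power loss is 0.2 to 0.4 points.

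**How large is 5 points?** For 30 to 50% specialised, the stratum variance is 5.25 to 6.25, which is 47 to 56% of 11.25. At 3 points it is 1.89 to 2.25, or 17 to 20%.

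**The case against.** Several objections carry weight.

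- **The stratum is not excluded.** The covariate list is open and specialisation is a described characteristic. Practices are randomised but the master is held by a person, so a practice may contain both kinds of physiotherapist, and uneven recruitment could bring the factor in through the imbalance rule. This stands, but either route leaves a design variable to later discretion.
- **The 5-point case is generous.** One binary factor would explain about half the variation between clusters, and nothing in the SAP supports that. Adjustment for baseline function, pain and fears could absorb part of any stratum effect. This stands, so 5 points is labelled an upper scenario.
- **The mechanism needs a cluster effect the SAP does not state.** This stands; without one the loss nearly vanishes.

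A reader might infer that the omission biases the treatment effect or inflates type I error. It does neither: the estimate is unchanged under balance, and omission lowers the rejection rate under the null.

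A reader might also infer that the remedy must include REML with a small-sample df correction, and that the whole package recovers precision. It does not. In the 5-point scenario, moving from ML with a normal reference and no stratum to REML with t on 17 df and the stratum takes power from about 0.920 to 0.900 and the CI half-width from 5.84 to 6.20. The estimator question is about type I error with few clusters: ML with a normal reference gives about 0.06 to 0.07 when the stratum effect is small or the stratum is included. It is a separate point and does not carry this one. The wording of the imbalance rule for other covariates does not carry it either.

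**Conclusion.** The point holds as a minor one. The SAP stratifies on the psychosomatic master, does not name it in the models, and gives physiotherapist characteristics an entry rule that is poorly suited to a stratified factor. If the stratum is prognostic and clusters are modelled, the reported standard error is too large. On the cluster-mean t-test with 20 clusters of 6, the cost runs from nothing (no stratum effect) through about 1 power point (3 ODI points) to about 3 points with a CI some 6 to 8% wider (5 ODI points). It would be larger with fewer, bigger clusters and negligible if no cluster effect is fitted. The stratum effect, the proportion specialised and the number of clusters are assumptions; the SAP does not state the number of practices. Repeated measures were not modelled.

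**What to change.** In Primary analysis, state that completion of the psychosomatic master, coded exactly as used at randomisation, is a fixed effect in the model regardless of observed balance. Repeat this for the secondary models, or let it carry over explicitly.

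The change is SAP wording only, since the variable is known from randomisation. It spends one between-cluster degree of freedom: about 0.2 to 0.3 power points with 20 clusters if the stratum has no effect, and about 1.7 points if there were only 10 practices (0.729 v 0.712).

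The df method should be settled separately, but with this change in view. If plain ML with a normal reference is kept, adding the term in the 5-point scenario moves type I error from about 0.05 to about 0.06 (ICC including the stratum) or 0.07 (ICC excluding it).
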